5.6 Reliability

To ensure consistency, validation checks of the data will be conducted. This will include checking for duplicate records, checking the range of variable values and validating potential outliers where possible (referring back to sites if necessary). As the data is collected electronically, many of these checks will be implemented automatically as part of the data entry procedure. Calculations and processes performed by a computer program, including the construction of derived data, will be checked by hand calculations. These checks will also confirm whether the data has been imported into the statistical software correctly and will check any merging of different datasets. Clarification will be sought from the trial office in the case of discrepancies.

For each variable, missing value codes will be checked for consistency and proportion of missing values per variable will be presented. Patterns of missing data will be explored. Where missing data imputation is used, imputed values will also be verified using the validation techniques described above.

6. ANALYSIS

The primary estimand of interest will be a treatment policy estimand (ITT population), using data from all randomised participants as randomised. This is chosen as the primary estimand to reflect the pragmatic nature of the study, and to identify the treatment effect regardless of any intercurrent events occurring. The elements of the primary estimand are summarised in Table 1.

The protocol also mandates a per-protocol analysis. The per-protocol analyses (section 4.2) will include all randomised participants who received their allocated treatment but excludes those randomised participants who were found ineligible post-randomisation, did not receive their allocated treatment.

Treatment switching as defined by NICE refers to the situation in a randomised controlled trial where patients switch from their randomly assigned treatment onto an alternative. Although it is widely recognised that ITT does not identify the true comparative effectiveness of the treatments under investigation there is disagreement on the acceptability of adjustment methods that can be used. Following NICE recommendations our ITT analyses is supplemented with further analyses in an attempt to adjust for switching [16] and described in section 6.4 sensitivity analyses.

The primary analysis and sensitivity analysis described in sections 6.2-6.4 focus on the primary estimand detailed in Table 1 which targets the average difference in PROMIS scores (ATE) between the two interventions in the combined groups randomised to receive each intervention. The resulting treatment effect represents the average difference in PROMIS scores we can expect if all participants in the target population were treated with non-operative treatment instead of being treated with operative fixation [17-19].

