5.2 Evidence why this research is needed now

The clinical management of any fracture depends upon several factors, including the severity of the fracture and the personal characteristics of the patient. These variables are generally out of the control of the treating surgeon. However, the decision to offer 'operative intervention' is highly dependent upon the surgeon, and indeed patients expect their surgeon to advise them in this area.

Not only is there controversy whether to operate on this injury, the indications amongst those receiving surgery vary considerably. There is agreement that in those instances where the fragment of medial epicondyle is trapped in the joint or where the elbow is dislocated and in need of operative intervention to realign the bones, then surgery must be undertaken. However, beyond these relatively rare indications, the usual indication for surgery is radiographic displacement of the fracture fragments beyond a surgeon-dependent threshold that varies between 2mm and 15mm^{6,7}; however radiographs on which this assessment is made are known to be hugely misleading with 'minimally displaced' fractures frequently having >10mm displacement evident when using 3D imaging^{8,9}. In routine clinical practice 3D imaging is not routinely performed for this injury. In instances whereby the fracture is associated with an elbow dislocation, and the elbow can be relocated with the bones realigned in the emergency department, there is controversy as to whether this necessitates fixation irrespective of the degree of fracture displacement, however a recent systematic review did not find evidence to support the need for surgery in this instance³. The degree of displacement, either initially or after healing, has not been shown to affect the outcome of treatment.

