Complications - All complications will be recorded. Particular note will be made of complications related to the cast (e.g. pressure areas) or surgery (e.g. pain, wound infection, injury/irritation to the ulna nerve, implant irritation, screw cut-out, broken or retained metalwork and the subsequent need to remove metal pins/screws), including hospital admission to manage these complications. Additionally, any digital images of the elbow that have been collected as part of routine practice will be harvested from PACS at the end of the study and uploaded to the study database in jpg, png or gif format. In particular, we will seek to identify images collected pre-operatively, intra-operatively (where relevant) and the last available follow-up image (i.e. the most recent image collected prior to the 1year primary outcome point - although we acknowledge that this may have been some weeks/months prior to this time-point). No specific imaging is required at any stage as part of the protocol for this study. Collection of routine digital images as described above has been reviewed by the Radiation Assurance HRA who indicated that the harvesting of routine images in this manner does not constitute exposure to radiation – passing their test "if the radiographs were not available, would the PI require that they took place". In Australia, the RCH Radiation Safety Officer has confirmed that the imaging involves radiation exposure that is considered standard care for these participants and no specific radiation risk statement is required in the information provided to research participants. Where available, these images will be used to make an assessment of the quality of the reduction, and the presence of bone union.

Healthcare Utilisation – This will be monitored for the economic analysis. Unit cost data will be obtained from national databases such as the BNF and PSSRU Costs of Health and Social Care. Where these are not available the unit cost will be estimated in consultation with the Oxford University Hospitals finance department. NHS/Medicare/NHI visits and out-of-pocket expenses from families will be recorded via a short questionnaire which will be administered at 3, 6 and 12 months post randomisation completed by the parents/guardians.

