7.3 Methodology

7.3.1 Screening and Eligibility

Patients will be eligible for this study if:

- There is radiographic evidence of a displaced medial epicondyle fracture of the Humerus, with fracture displacement determined by the surgeon as per their usual clinical practice.
- They are aged between 7 and 15 years old inclusive.

Patients will be excluded from participation in this study if:

• The injury is more than two weeks old.

- There is incarceration of the medial epicondyle fragment within the elbow joint.
- The injury is part of a complex elbow fracture (i.e. fracture extending into the joint).
- There are other fractured bones elsewhere in the body, in addition to the elbow injury.
- The elbow, if dislocated, is unable to be realigned into a satisfactory position in the emergency department.
- There is evidence that the patient and/or parent/guardian would be unable to adhere to trial procedures or complete follow-up, such as insufficient English language comprehension, developmental delay or a developmental abnormality or no access by parents to the internet.

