7.4 Technologies assessed

All of the hospitals involved in this trial are familiar with both techniques. All surgeons are proficient in the surgical techniques. All of the patients will receive analgesia at the discretion of the treating clinician as per local guidelines. In the absence of local guidelines clinicians should follow best practice recommendations from national bodies, such as the Royal College of Emergency Medicine best practice guidelines for the management of acute pain in children²¹. If the elbow is dislocated on arrival in the emergency department, clinicians may attempt to restore the alignment of the elbow using their preferred reduction manoeuvres with appropriate analgesia and/or sedation, as per usual clinical practice.

This trial will compare two approaches to treat displaced medial epicondyle of the humerus in children:

7.4.1 Operative Fixation;

Children are admitted to hospital for surgery, which typically is scheduled on a daytime trauma operating session, though patients can be enrolled irrespective of the time of presentation/ surgery. Children undergo a general anaesthetic. After the skin has been covered in antiseptic, an incision will be made over the medial epicondyle paying particular attention to the location of the ulna nerve. The bone fragments will be opposed in the optimal position achievable under direct vision. A record will be made of the type of fixation used. The bone fragments will be fixed using the preferred technique of the surgeon (i.e. screw/ wire(s)). Although, the basic principles of fixation are inherent in the technique, there are several different options available to the surgeon, with the most common being screw fixation. The type of implant, size and insertion technique are not believed to affect the outcome, and will be left entirely to the discretion of the surgeon as per their normal practice. At the end of the procedure, a sling/plaster/splint/bandage will be applied as per the standard surgical practice. The elbow will be allowed to mobilise as per the usual practice of the treating surgeon under the direction of the clinical team, though fixed immobilisation in a cast should not be used for more than 4 weeks post randomisation.

7.4.2 Non-operative treatment;

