4.2 Definition of Analysis Populations

Populations for analysis are defined as follows:

- Intention-to-treat (ITT): all participants analysed in their randomised groups, regardless of actual treatment received. This reflects the primary estimand of interest (treatment policy).
- Per-Protocol (PP): participants who received the intervention as intended will be analysed according to the treatment they actually received. Participants will be excluded from the per-protocol population if:

- They did not receive the treatment allocated through randomisation
- o They did not fully satisfy the eligibility criteria for the study

Blinded review of the protocol deviation data (not separated by treatment arm) which may affect the PP analyses will be undertaken prior to the final data lock. A summary of the characteristics of exclusions to define the per-protocol population will be reported. The motivation for any such exclusion is to examine the robustness of inferences to factors that can threaten the study's internal validity. Deviations associated with intercurrent events which occurred in the trial setting but would not be observed in practice are considered the main threat, consistent with the primary ITT estimand. If a significant number of such deviations are present e.g. involving more than >5% of participants, the results of the primary analyses may introduce ambiguity in the interpretation. In this case sensitivity analyses is undertaken and detailed in section 6.4.

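### The per-protocol rule lets ineligibility found after randomisation remove a child, and only the operative arm has the fracture opened to view, so exclusion can depend on the arm

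*SAP*

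**What the plan says.** SAP section 6 (Analysis) describes a per-protocol analysis that "excludes those randomised participants who were found ineligible post-randomisation, did not receive their allocated treatment". SAP 4.2 lists as one ground for exclusion: "They did not fully satisfy the eligibility criteria for the study". Neither section gives a time limit, names the evidence to be used, or asks for equal ascertainment in the two arms.

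Protocol 7.3.1 includes among its exclusion criteria: "There is incarceration of the medial epicondyle fragment within the elbow joint". A complex fracture that reaches the joint is another. Both are to be applied at screening. Protocol 7.3.6 foresees that some patients may be judged ineligible after consent, and says they are not replaced.

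For the operative arm, Protocol 7.4.1 describes an incision and says: "The bone fragments will be opposed in the optimal position achievable under direct vision". In the non-operative arm (7.4.2) the elbow is immobilised and nothing is opened. On imaging, Protocol 6.3 says: "No specific imaging is required at any stage as part of the protocol for this study". Protocol 5.2 adds: "In routine clinical practice 3D imaging is not routinely performed for this injury".

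Protocol 10.1 gives the per-protocol analysis the job of testing how robust the results are. Both documents warn in general terms that it may be biased because randomisation is no longer preserved. SAP 4.2 plans a blinded review of deviations, pooled over arms, and a summary of the characteristics of those excluded.

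**The concern.** A child whose incarceration or joint extension was missed at screening can be allocated to either arm. In the operative arm the surgeon opens the fracture and may see it. If the fragment is then fixed, the child has received the allocated treatment, so only the eligibility rule removes that child from the per-protocol set. A child with the same unrecognised feature in the cast arm has no equivalent moment of discovery built into treatment and may stay in.

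Membership of the set would then depend on the arm through information that arises after randomisation. This is different from treatment switching, which SAP 6.4 addresses.

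The existing safeguards do not reach it. The pooled blinded review looks at deviations already detected, whereas the imbalance arises at detection. The tables in the SAP would not clearly show it either:

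- Table 2 covers patients who were not randomised.
- Table 3 splits deviations by arm, but by impact and importance, not by how they were found.
- Table 8 gives reasons only for children who did not receive the allocated treatment.

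At stake is the comparison of the per-protocol result with the primary result. A robustness check should not carry an avoidable selection of its own.

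**Working it through.** **The plan's figures.** The documents give no figure for late-found ineligibility, overall or by arm. Two related figures can be checked.

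- Audit (Protocol 5.1): 39/520 = 7.5%, printed as 8%. This is the share of incarcerated fragments among all fractures, before any trial exclusion.
- Sample size (SAP 3.3): a difference of 4, SD 10, two-sided 5% and 90% power give 132 per arm by the normal approximation and 132.3 by the t-test. That rounds up to the stated 133 per arm, 266 in total. With 20% loss, 133/0.8 = 166.25, so 167 per arm and 334 recruited. The stated figures reproduce.

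**Model of the selection.** Let p be the share of randomised children with an unrecognised exclusion and D their deficit in T-score points at 12 months. Let s1 and s0 be the shares of those children detected and removed in the operative and cast arms. The shift in the per-protocol difference towards surgery is

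shift = D × [ p(1 − s0)/(1 − p·s0) − p(1 − s1)/(1 − p·s1) ].

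None of p, D, s1 and s0 is in the documents. All are assumptions. The range for p is 1% to 7.5%; the top end is the audit rate before screening, so it is an upper bound for incarceration.

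**Worst case, s1 = 1 and s0 = 0.** The formula reduces to p × D. With D = 10:

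| p | Removed from 167 operative children | Shift (points) |
|---|---|---|
| 1% | 1.7 | 0.10 |
| 2% | 3.3 | 0.20 |
| 5% | 8.4 | 0.50 |
| 7.5% | 12.5 | 0.75 |

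At p = 7.5%, D = 5 gives 0.38 and D = 15 gives 1.13.

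**Half also detected in the cast arm, s1 = 1 and s0 = 0.5.** At p = 7.5% and D = 10: 10 × 0.0375/0.9625 = 0.39. At p = 1%: 10 × 0.005/0.995 = 0.05.

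**Equal detection, s1 = s0.** The two terms cancel and the shift is 0.

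**Scale.** With SD 10 and 133 per arm, the standard error of a simple difference in means is 10 × √(2/133) = 1.23. The 0.1 to 0.75 range is therefore about 0.1 to 0.6 standard errors. A 4-point shift at p = 7.5% would need D = 4/0.075 = 53 points, more than the 48-point width of the 10 to 58 scale given in SAP 6.1. The loss of numbers matters little: cutting the operative arm by 7.5%, from 133 to 123, lowers power from 90.4% to 89.2%.

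**The case against.** A reader might infer that the rule does remove severe injuries mainly from the operative arm, and that the per-protocol result is therefore biased in favour of surgery. The documents do not support that, for these reasons.

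- Both features are screening exclusions and have rows in the SAP's screening table. The plan treats them as recognisable before randomisation. Nothing says they can be recognised only at surgery, and no missed rate is given.
- Protocol 5.2 says that "radiographs on which this assessment is made are known to be hugely misleading", but the subject there is the degree of displacement. It is not evidence that trapped fragments or joint extension are missed.
- Cast-arm children can leave the set too. They have a routine 4-week appointment, complications and further surgery are followed up, and routine images are collected in both arms. A cast child whose incarceration was recognised and operated on could leave as not having received the allocated treatment.
- That affected children do worse at 12 months is an assumption, and the direction of any shift depends on it.
- The analysis is supplementary, its general risk of bias is declared, and the primary analysis keeps all randomised children.

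All of this stands, and it limits the size and certainty of the point. It does not supply the missing limit on timing and evidence, and it does not make detection equal between the arms. It is also fair to say that keeping known ineligible children in a per-protocol set is one convention among several. The reason to choose it here is that the alternative makes membership depend on what each arm's treatment reveals.

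**Conclusion.** The point holds as a risk. SAP 4.2 and 6 leave the timing and source of eligibility evidence open, and only operative treatment exposes the fracture, so per-protocol exclusion can depend on the arm. How often this would happen, and how it would balance between the arms, is unknown.

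The 0.1 to 0.75 point range rests on three assumptions: 1% to 7.5% affected, a 10-point deficit, and complete detection in one arm with none in the other. The top of the range takes a rate measured before screening, so for incarceration it supposes that screening catches nothing. No plausible value produces a 4-point effect. The upper values could blur a close comparison of the per-protocol and primary results. This is a modest improvement to a supplementary analysis, worth making because it is cheap.

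**What to change.** Align SAP 4.2 and 6 on one rule with three parts:

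1. A per-protocol eligibility exclusion rests only on a fact present before randomisation and established from the existing pre-randomisation screening records. It is applied alike in both arms, and no images need to be re-read.
2. A finding first made at operation or later does not by itself remove a child from the per-protocol set. The separate exclusion for not receiving the allocated treatment stays as it is.
3. Per-protocol exclusions and late-found ineligibility are reported by arm, with the reason and how each was detected.

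With equal ascertainment, the shift from this mechanism is zero. The cost is a few sentences and one small table, with no new data collection. The downside is that a few truly ineligible children remain in the per-protocol set; the listing in part 3 makes the known ones visible.

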6.1 Outcome Definitions

Primary Outcome PROMIS Upper Extremity: measured pre-randomised (baseline), 4 weeks (routine follow-up) and then at 6 weeks, 3 months, 6 months and 12 months via electronic collection.

The primary outcome for this study is the functional recovery assessed using the Patient Report Outcomes Measurement Information System (PROMIS Bank v2.0: Upper Limb Score for Children Computer Adaptive Test (CAT) – PROMIS is a collection of patient-reported health status tools available for children and adults that were developed to be disease non-specific in collaboration with the USA National Institute for Health [20, 21]. This is a bounded score on a standardised scale (T-score) in the interval [10 – 58] (https://www.healthmeasures.net/images/PROMIS/manuals/Scoring_Manual_Only/PROMIS_Physical_Funct ion_User_Manual_and_Scoring_Instructions_05Dec2023.pdf). These tools can be administered to healthy children, as well as to children with a variety of chronic health conditions. They are generally self-reported from the age of eight years, and proxy-reported below eight years. The PROMIS Paediatric item banks were developed using a strategic item generation methodology adopted by the PROMIS Network using item response theory. Field-testing occurred among 4,129 children aged eight to 17 years old [22]. All raw scores generated from PROMIS instruments are translated into standardized T-scores with a population mean of 50 and a standard deviation (SD) of 10. The population mean refers to the mean of the calibration sample, which, for paediatric and parent proxy instruments, is composed of a higher percentage of patients with chronic illness. Lower T scores indicate a worse outcome for upper limb function. PROMIS is available in full (30 questions), short-form (eight questions), or as a computer adaptive test 'CAT' (average eight questions). A CAT

enables the answer from one question to inform the choice of the next so that each child completing a CAT could answer a distinct set of questions to arrive at their score.

Secondary Outcomes

Sport/Performing Art Module of DASH: measured pre-randomised (baseline), 4 weeks (routine follow-up) and then at 6 weeks, 3 months, 6 months and 12 months via electronic collection.

This is a tool for recording details of sports and performing arts participation relating to upper limb function. Although not specifically developed in children, there was universal agreement, among children present at an 'Elbow Study Day' and members of the NIHR YPAG, that the language in this tool was appropriate for use among children who are able to comprehend other self-reported questionnaires used in this study [23].

Wong-Baker FACES Pain Rating Scale: measured pre-randomised (baseline), 4 weeks (routine follow-up) and then at 6 weeks, 3 months, 6 months and 12 months via electronic collection.

This is a validated self-reported ordinal assessment of pain [24] using a series of six facial expressions to illustrate pain intensity. A numerical rating is assigned to each face (from 0, "no hurt" to 10, "hurts worst"). It has been validated [25] for use among children from five years old. It is highly correlated to the visual analogue scale (r = 0.90, p < 0.001) and is widely used in clinical practice, forming part of the Royal College of Emergency Medicine 'Composite tool for the assessment of pain in children,'

(https://rcem.ac.uk/wp-

content/uploads/2021/11/Pain_in_Children_2017_18_National_Report_Oct_2018.pdf (date last accessed 18 January 2024) and recommended in the NICE major trauma guidelines (https://www.nice.org.uk/guidance/ng39).

Quality of life (EQ-5D-Y): measured pre-randomised (baseline), 4 weeks (routine follow-up) and then at 6 weeks, 3 months, 6 months and 12 months via electronic collection.

This is the child-friendly version of the EQ-5D-3L, which has been adapted in terms of language for children aged eight to 11 years and for adolescents aged 12 to 18 years. A proxy version is available for younger children. Its age appropriateness in terms of feasibility, reliability, and validity in children and adolescents has been established [26, 27]. At the time of finalising this SAP, the adult value set is available and will be used. The HEAP will include supplementary analysis using available child value sets.

Complications: All complications are recorded at the 4-week routine follow-up and then at 6 weeks, 3 months, 6 months and 12 months via electronic collection.

Particular note will be made of complications related to the cast (e.g. pressure areas) or surgery (e.g. pain, wound infection, injury/irritation to the ulna nerve, implant irritation, screw cut-out, broken or retained metalwork, and the subsequent need to remove metal pins/screws), including hospital admission to manage these complications. These are summarised in the Table below.

Table 10: Comparison of complications & SAEs between treatment allocations

| | Operative fixation | Non-operative treatment | | OR (95 | 5% CI) | p- value |
|--|-----------------------|----------------------------|---|--------|--------|-------------|
| | n % | n | % | Raw | Adj. | |
| Number of complications* | - | | - | - | - | - |
| Participants with complications | | | | | | |
| Wound problems (from surgery*) | | | | | | |
| Elbow stiffness | | | | | | |
| Unable to move fingers normally | | | | | | |
| Patient Reported concerns | | | | | | |
| Unable to feel fingers normally | | | | | | |
| Ulna nerve problems (little & ring | | | | | | |
| fingers) | | | | | | |
| Other | | | | | | |
| Intra-operative complications | - | | - | - | - | - |
| Participants with intra-operative | | | | | | |
| complications | | | | | | |
| Ulna nerve injury | | | | | | |
| Fragmentation of bone | | | | | | |
| Wire breakage | | | | | | |
| Anaesthesia complications | | | | | | |
| Post-operative bleeding | | | | | | |
| Screw cut-out | | | | | | |
| Other | | | | | | |
| Immobilisation complications | - | | - | - | - | - |
| Participants with immobilisation | | | | | | |
| complications | | | | | | |
| Skin complication owing to pressure | | | | | | |
| area | | | | | | |
| Discomfort | | | | | | |
| Other | | | | | | |
| Unplanned surgery/hospital | - | | - | - | - | - |
| admissions* | | | | | | |
| Participants with unplanned | | | | | | |
| surgery/hospital admissions | | | | | | |
| Fracture fixation/ revision fixation | | | | | | |
| Removal of screw(s)/wire(s) | | | | | | |
| Planned removal | | | | | | |
| Irritation | | | | | | |
| Other | | | | | | |
| Nerve exploration (isolated | | | | | | |
| procedure) Nerve exploration & screw/wire | | | | | | |
| adjustment | | | | | | |
| Nerve exploration and grafting | | | | | | |
| Debride wound/ wound infection | | | | | | |
| Microbiological confirmation of | | | | | | |
| infection | | | | | | |
| Antibiotics prescribed | | | | | | |
| Other | | | | | | |

| | Operative fixation | | Non-operative treatment | | OR (95% CI) | | p- value |
|--------------------------------------|--------------------|---|----------------------------|---|-------------|------|-------------|
| | n | % | n | % | Raw | Adj. | |
| Number of unforeseeable SAEs* | | - | | - | - | - | - |
| Participants with unforeseeable SAEs | | | | | | | |

Radiographic outcomes and analysis will be considered in a separate document to this analysis plan.

Healthcare use: will be reported in the economic analysis and will include: missed school attendance at 6 weeks, 3 months, 6 months and 12 months and resource utilisation at 3 months, 6 months and 12 months [8]. The clinical report will only include comparative school attendance at 6 weeks, 3 months, 6 months and 12 months.

